#### **8.2.8. Head-Lift Duration through Day 7**

The number and proportion of subjects who are able to hold their head up for 5 seconds will be tabulated by treatment arm and visit.

A logistic generalized linear mixed model will be used to analyze the change from baseline to Day 7. Analyses will include the fixed effect of treatment as the covariate of interest, with baseline head-lift duration, age group, baseline neurotoxicity, visit (categorical), and visit by treatment interaction as covariates. The model will be used to estimate the effect of treatment on head-lift duration at each assessment time point through Day 7. LS means at each assessment time point will be calculated and tabulated from the model.

Only subjects with an SSS nervous system subscore  $\geq 2$  at baseline will be included in the analysis.

#### **8.2.9. Total Duration of Ventilatory Support from Baseline through Day 28**

The number and percent of subjects who need ventilatory support and the duration of time from initiation of ventilatory support to initiation of weaning will be tabulated by treatment arm. The time from initiation of ventilatory support to initiation of weaning will be compared using the Wilcoxon Rank Sum Test.

If the number of patients receiving ventilatory support is less than 5, this outcome will be reported descriptively.

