13.1.4 Efficacy Analysis

13.1.4.1 Primary Efficacy Endpoints

Statistical analysis of efficacy will be assessed by an improvement in the composite SSS (See SAP for SSS scale; Individual Category Severity Assessments: Pulmonary, Cardiovascular, Hematologic Symptoms, Renal, and Nervous Systems) from Baseline (pre-dosing) to 6 and 9 hours after first dose, where the average of the 6- and 9-hour scores are used as the post treatment value: Change = (Baseline – [6hr + 9hr]/2). Subjects that die before recording a 6 or 9 hour SSS measurement will be assigned the worst possible score when analyzing the primary endpoint. Missing measurements of the SSS at 6 or at 9 hours won't be replaced for the purpose of calculating the primary outcome. If the SSS at one of these timepoints is missing, the average SSS will be based solely on the SSS recorded for the other time point.

13.1.4.2 Secondary Efficacy Endpoints

The secondary efficacy endpoints are to evaluate the:

- AUC of the pulmonary, cardiovascular, hematologic symptoms, renal, and nervous system sections of the SSS from Baseline through Day 7
- Complete SSS from Baseline through Day 7
- SSS neurologic system subscore from Baseline through Day 3
- Coagulation abnormalities from Baseline through Day 7
- Hemolysis markers from Baseline through Day 3
- Levels of the myonecrosis marker, creatine kinase (CK), from Baseline through Day 3
- Numeric Pain Rating Scale (NPRS) score in patients able to respond from Baseline through Day 28
- Kidney function markers from Baseline through Day 28
- Total differential antivenom requirement from Baseline through Day 28
- Head-Lift duration from Baseline through Day 7
- Total duration of ventilatory support from Baseline through Day 28
- Total duration of Intensive Care Unit (ICU) stay from Baseline through Day 28
- Total duration of hospitalization from Baseline through Day 28
- All-cause mortality from Baseline through Day 28
- Clinical Global Impression-Improvement (CGI-I) from Baseline through Day 7
- Patient Global Impression of Change (PGIC) from Baseline through Day 7
- Patient-Specific Functional Scale (PSFS) total score from Baseline through Day 28

13.1.4.3 Exploratory Endpoints

The exploratory efficacy endpoints are to evaluate the:

- Change in the SSS from Baseline through Day 7 using compressed SSS scale
- SSS from Baseline through Day 28 after first dose
- Grip strength pre-dosing through Day 28

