#### **6.1.7.8. Time from Initiation of Ventilatory Support to Initiation of Weaning**

The total time from initiation of ventilatory support to initiation of weaning will be calculated in hours. Subsequent re-intubations will not be included in this calculation.

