#### **6.1.7.9. Duration of Ventilatory Support**

The duration (hours) of ventilatory support for primary neurotoxic envenoming will be calculated as the total duration of mechanical (ventilator) or manual (bag valve mask) methods used to assist or replace spontaneous respiration. If a subject is reintubated one or more times, these additional periods of ventilatory support (from initiation of ventilatory support to extubation or removal of ventilatory support) will be included as part of the total time.

$$\sum_{\text{for each ventilation}} (\text{time of removal of support} - \text{time of initiation of support})$$

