#### **6.1.7.10. Duration of ICU Stay**

The length of ICU stay from baseline to Day 28 will be calculated using the following duration in hours

$$\sum_{\text{for each episode}} (\text{ICU discharge date and time} - \text{ICU admission date and time})$$

The duration of ICU stay will be truncated at Day 28. If a discharge date and time is after Day 28, it will be replaced by Day 28.

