#### **6.1.7.11. Duration of hospitalization**

The length of hospital stay from baseline to Day 28 will be calculated using the following duration in hours

$$\sum_{\text{for each admission}} (\text{discharge date and time} - \text{admission date and time})$$

The duration of hospitalization will be truncated at Day 28. If a discharge date and time is after Day 28, it will be replaced by Day 28.

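### SAP 8.2.9 analyses time to start of weaning under the name of total duration of ventilatory support, and the variable derived for that endpoint is used in no section 8 analysis

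*SAP*

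**What the plan says.** Protocol 13.1.4.2 lists the secondary endpoint as "Total duration of ventilatory support from Baseline through Day 28". SAP 2.2.1.3 repeats it, and SAP 8.2.9 uses it as its title. Neither list of endpoints contains time to weaning.

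The SAP derives two ventilation variables:

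- **6.1.7.8** runs from the start of support to the start of weaning, in hours. It adds: "Subsequent re-intubations will not be included in this calculation".
- **6.1.7.9** sums, over every ventilation episode, the time from start to removal of support. It brings in later episodes: "If a subject is reintubated one or more times, these additional periods of ventilatory support" are part of the total.

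The analysis text of 8.2.9 tabulates how many subjects need support and the time to weaning, then tests the latter: "The time from initiation of ventilatory support to initiation of weaning will be compared using the Wilcoxon Rank Sum Test". If fewer than 5 patients are ventilated, the outcome is only described. SAP 8.2 says that these other secondary analyses are read as exploratory.

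**The concern.** A reader of the study report will take the result in 8.2.9 to be the protocol's total-duration endpoint. It would in fact be a shorter interval that omits the weaning period and everything after a failed extubation. A patient who is weaned early and then re-intubated for days would look better than one weaned later and extubated once. Even if only descriptive statistics are produced, they would carry the wrong label, because 8.2.9 tabulates time to weaning and not the total.

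The titles of Tables 14.2.12.1 to 14.2.12.5 add to the confusion. They refer to durations of ventilatory support, next to ICU and hospital stay, and cite neither derivation. A programmer working from 8.2.9 and one working from 6.1.7.9 could fill the same table with different numbers.

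**Working it through.** **Which variable is used where**

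| Place | Variable |
|---|---|
| Protocol 13.1.4.2; SAP 2.2.1.3 | Total duration, Baseline through Day 28 |
| SAP 8.2.9, title | Total duration, Baseline through Day 28 |
| SAP 8.2.9, tabulation and test | Time to start of weaning (6.1.7.8) |
| SAP 6.1.7.9 | Total duration; used in no section 8 analysis |
| Tables 14.2.12.1 to 14.2.12.5, titles | Ventilatory support durations; derivation not stated |

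The neighbouring section on ICU stay (8.2.10) tests the variable named in its title, so the mismatch is specific to ventilation. The Document History entry for version 3.0 records a change of test for hospital durations but no change of variable. Section 10 refers back to that history.

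**How far the two variables can differ**

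The documents give no ventilation, weaning or re-intubation rates. All hours below are therefore assumptions, with Baseline = 0.

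- Patient A: support starts at 0 h, weaning at 36 h, extubation at 48 h; re-intubated from 60 h to 132 h.
  - 6.1.7.8: 36 − 0 = 36 h.
  - 6.1.7.9: (48 − 0) + (132 − 60) = 48 + 72 = 120 h.
  - Not counted by 8.2.9: 120 − 36 = 84 h, made up of 12 h of weaning and 72 h of re-intubation; 84/120 = 70%.
- Patient B: support starts at 0 h, weaning at 60 h, extubation at 72 h, no re-intubation.
  - 6.1.7.8: 60 − 0 = 60 h.
  - 6.1.7.9: 72 − 0 = 72 h.

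On time to weaning A ranks below B (36 < 60). On total duration A ranks above B (120 > 72). A rank test therefore sees the pair in opposite order.

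To show the range, let A's re-intubation last r hours. A's total is 48 + r, and the share not counted is (12 + r)/(48 + r).

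- r = 0: total 48 h, 12/48 = 25% not counted, same order as time to weaning.
- r = 24: total 72 h, 36/72 = 50% not counted, tied with B.
- r = 72: total 120 h, 70% not counted, order reversed.

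The order reverses for any re-intubation longer than 24 h in this pair. Even without re-intubation, the weaning period is lost.

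**Whether 6.1.7.9 can be used as it stands**

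It needs three repairs to match the endpoint's name.

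1. *Start.* Its formula counts from the start of support. Protocol 10.2.2 provides for subjects already intubated at Baseline, so earlier time can enter. Patient C, with support from −5 h to 20 h, gets 20 − (−5) = 25 h; the time from Baseline is 20 h.
2. *End.* It has no Day 28 cut-off. For ICU stay, 6.1.7.10 says "If a discharge date and time is after Day 28, it will be replaced by Day 28"; for hospital stay, 6.1.7.11 says "The duration of hospitalization will be truncated at Day 28".
3. *Scope.* It is restricted by cause: "The duration (hours) of ventilatory support for primary neurotoxic envenoming will be calculated as the total duration". The endpoint name has no such restriction.

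**Related gaps**

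The SAP gives no rule for when weaning starts. Protocol Appendix C7 notes that some newer ventilator modes serve more than one phase. 6.1.7.9 also counts "manual (bag valve mask) methods used to assist or replace spontaneous respiration", for which the documents describe no start of weaning. Section 8.2.9 does not say whether never-ventilated patients enter the test or how deaths are handled.

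**The case against.** - **Time to weaning may be deliberate.** Protocol 10.3.1.7 recognises that extubation can be postponed by institutional practice, so the start of weaning may be the cleaner clinical marker. That is a fair reason to choose it, but it is then a different endpoint and should be named as one.
- **The test itself is not ambiguous.** Section 8.2.9 names its variable for both tabulation and test, and 6.1.7.8 derives exactly that. This is correct: the conflict is between the instruction and the endpoint name, section title and table titles.
- **The total is not lost.** SAP 13.6 puts all calculated variables in listings, and one listing is titled for duration of support. With few ventilated patients this would show much of what matters. A by-subject listing is still not the analysis of a listed endpoint.
- **The test may never run.** SAP 8.2.2 reports unexpectedly few severely neurotoxic patients, so ventilated patients may be few. This limits the consequence but does not correct the label.
- **Lack of a declared change is weak evidence.** Earlier SAP versions are not available, and section 10 gives only examples. Accepted; the mismatch with the endpoint name stands without it.
- **Some side points are narrower than they look.** Appendix C7 has a category of weaning modes, and modes are collected in the CRF. The ICU and hospital formulas also do not clip explicitly at Baseline. Never-ventilated patients have no value for time to weaning, so how to treat them matters mainly once the total is analysed. These points reduce the secondary gaps, not the main finding.

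**Conclusion.** The concern holds. Section 8.2.9 analyses time to start of weaning under the name of total duration, and 6.1.7.9 is used in no section 8 analysis. This follows from the text and needs no numerical assumption. The two variables differ for every ventilated patient with a weaning period or a re-intubation, and they can reverse the order of patients. The 70% and the reversal illustrate what is possible under assumed hours; they do not estimate what will occur, and no effect on power is claimed. The consequence is low, because the endpoint is exploratory and outside the fixed sequence, and it may be reported only descriptively. It should still be corrected, since otherwise a protocol-listed endpoint is reported with a different variable. The missing definition of weaning and the handling of never-ventilated patients and deaths are lesser gaps, and the conclusion does not depend on them.

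**What to change.** Make one of two changes before unblinding.

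1. **Preferred.** In 8.2.9, tabulate the 6.1.7.9 total and apply the Wilcoxon test to it. Keep time to weaning as a separately labelled supportive summary, with a stated rule for when weaning starts. In 6.1.7.9, count only time from Baseline, truncate at Day 28 as 6.1.7.10 and 6.1.7.11 do, and reconcile the restriction to neurotoxic envenoming with the endpoint name.
2. **If time to weaning was intended.** Declare the change in section 10 and rename 8.2.9 and Tables 14.2.12.1 to 14.2.12.5 accordingly.

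Either way, state whether never-ventilated patients enter the test and how deaths are treated. Zero hours for the former and worst rank for the latter are options, but together they turn the endpoint into a composite that ICU and hospital stay do not use.

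The cost is a few sentences in 8.2.9 and 6.1.7.9, or in section 10 and the titles. The protocol asks sites to record pulmonary support interventions but does not name start and stop times. The 6.1.7.9 formula needs them, so check first that the eCRF holds them.

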Analysis of the secondary endpoints will be carried out for the ITT population.

All secondary endpoints will be summarized using frequencies and percentages for categorical endpoints, and numeric summary statistics for quantitative endpoints.

Additional ANCOVA or a repeated measures model (MMRM) analyses will be considered for quantitative secondary endpoints.

All-cause mortality will be analyzed using Kaplan-Meier methods.

PGI-C and CGI-I responders will be summarized by frequency and percentage at each visit within treatment group. The difference in treatment response will be analyzed using a logistic regression model at each visit with baseline SSS score, age group (5 to < 18 and \geq 18 years), neurological system subscore \geq 2 (Yes or No), and completion of the initial dose of antivenom prior to initiation of study drug (Yes or No) as covariates.

Additional details of the efficacy analyses will be given in the final SAP.

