### 2.2.1.3. Other Secondary Endpoints

The study has the following other secondary efficacy endpoints:

- Complete SSS from baseline (pre-dosing) through Day 7
- SSS neurologic system subscore from Baseline through Day 3
- Coagulation abnormalities from Baseline through Day 7
- Hemolysis markers from baseline through Day 3
- Levels of the myonecrosis marker, creatinine kinase (CK), from Baseline through Day 3
- Numeric Pain Rating Scale (NPRS) score in subjects able to respond from Baseline through Day 28
- Kidney function markers from baseline through Day 28
- Head-Lift duration from Baseline through Day 7
- Total duration of ventilatory support from Baseline through Day 28
- Total duration of Intensive Care Unit (ICU) stay from Baseline through Day 28
- Total duration of hospitalization from Baseline through Day 28
- All-cause mortality from Baseline through Day 28
- CGI-I scale from Baseline through Day 7
- PGIC from Baseline through Day 7
- Patient-Specific Functional Scale (PSFS) total score from Baseline through Day 28

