Note: The effect of varespladib on neurotoxicity is supported by the observation that varespladib prevents, reverses, or delays lethality from venom neurotoxicity in animals experimentally envenomed with Mojave rattlesnake, coral snake, krait, and taipan venoms even when administered at a point when weakness is refractory to antivenom reversal (e.g., Prasarnpun 2005; Anil et al. 2010; Lewin et al. 2018a, 2018b; and Gutierrez et al. 2021). Neurologic outcomes were not selected as the focus of the primary or key secondary efficacy endpoints because of the unexpectedly small number of severely neurotoxic patients enrolled in the trial.

### 8.2.3. Coagulation Abnormalities from Baseline through Day 7

Each of the four coagulation lab values (PT, PTT, platelets, and fibrinogen) will be analyzed using a proportional odds logistic regression with five ordered categories. Categories for the lab values in each of these analyses will use those defined by the Snakebite Severity Score (Dart et al. 1996), with normal lab values receiving a score of 0 and abnormal lab values receiving a score of 1 to 4 based on the following published cutoffs.

Coagulation Parameter	0	1	2	3	4	Units
Prothrombin Time	Lab validated reference range	Above lab ref range to 20 sec	>20 to 50 sec	>50 to 100 sec	Unmeasureable or above 100 sec	Sec
Partial Thromboplastin Time	Lab validated reference range	Above lab ref range to 50 sec	>50 to 75 sec	>75 to 100 sec	Unmeasureable or above 100 sec	Sec
Platelet count	Lab validated reference range	100,000 to ref	50,000 to <100,000K	20,000 to <50,000	Less than 20,000	/mL
Fibrinogen	Lab validated reference range	100 to ref	50 to <100	Less than 50	Undetectable	mg/dL

Analysis for each of the four coagulation parameters will be run separately for each time point from Day 1 3 hours to Day 7. The models will use the following covariates: baseline SSS score, age group (5 to 17 years,  $\geq$  18 years), baseline neurotoxicity, receipt of antivenom prior to baseline (Yes, No), and country. The treatment effect will be summarized with an estimated odds ratio and tested at a 5% two-sided significance level; the corresponding 95% two-sided confidence intervals will be presented. These analysis will only include subjects with lab value-specific coagulation abnormalities (hematology subscore  $\geq$  1 as derived from the relevant coagulation lab value) at baseline.

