### **8.2.10. Total Duration of ICU Stay from Baseline through Day 28**

Duration of ICU stay through 28 days post-baseline will be summarized by treatment arm. Duration will be measured in days.

The duration of ICU stay will be compared between treatment groups using the Wilcoxon Rank Sum Test.

If fewer than five patients report ICU stay, this outcome will be reported descriptively.

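### SAP 8.2.9 tests a ventilation time that exists only for ventilated patients, so the test cannot detect that ventilation was prevented

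*SAP*

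**What the plan says.** SAP 2.2.1.3 names the endpoint: "Total duration of ventilatory support from Baseline through Day 28". The test in SAP 8.2.9 uses a different variable: "The time from initiation of ventilatory support to initiation of weaning will be compared using the Wilcoxon Rank Sum Test". SAP 6.1.7.8 defines that variable: "The total time from initiation of ventilatory support to initiation of weaning will be calculated in hours". It then adds: "Subsequent re-intubations will not be included in this calculation". Neither section gives a value for a patient who was never ventilated, or for one who dies on the ventilator.

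SAP 6.1.7.9 defines a second variable, the summed ventilation time over all episodes including re-intubations. SAP 8.2.9 does not test it. Section 8.2.9 does tabulate how many patients in each arm needed ventilation, with no test, and sets a minimum count: "If the number of patients receiving ventilatory support is less than 5, this outcome will be reported descriptively".

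On population, Protocol 13.1.4.5 states: "Analysis of the secondary endpoints will be carried out for the ITT population". SAP 8.1.2 also assigns the secondary endpoints to the ITT population, and planned Table 14.2.12.1 carries that label. SAP 8.2 treats all of the other secondary analyses as exploratory.

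For ICU stay, SAP 8.2.10 has a similar minimum: "If fewer than five patients report ICU stay, this outcome will be reported descriptively". The variable there (SAP 6.1.7.10) is a sum over ICU episodes.

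**The concern.** A total duration has a natural value, zero, for a patient who never needed a ventilator. A time counted from the start of ventilation does not. Testing the second in place of the first changes both the question and the patients who answer it.

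The question becomes whether ventilated patients in the two arms took equally long to reach weaning. That null hypothesis can be true when the drug prevents most ventilation. It can also be false against the drug: if mainly the shorter cases are averted, those left on the drug arm are the longer ones.

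The patients become two subsets formed partly after randomisation. Other sections also restrict their analyses (hemolysis in 8.2.4, CK in 8.2.5, creatinine in 8.2.7, head-lift in 8.2.8), but each uses a baseline value, which keeps the comparison randomised. Ventilation that starts after dosing is not a baseline feature.

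At stake is the one formal comparison on ventilation. The protocol's scientific rationale (5.1.1) links venom neurotoxicity to rapid lethality and lists reversal of neurological effects among the hoped-for benefits, so averted ventilation is a plausible form of benefit.

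**Working it through.** **Inputs from the documents.** Enrolment up to 110, allocation 1:1 (SAP 3.2), so 110/2 = 55 per arm; two-sided alpha 0.05; Wilcoxon test and minimum of 5 ventilated patients (SAP 8.2.9). The documents give no ventilation rate, duration or power for this endpoint, so there is no stated figure to reproduce. The 94 evaluable patients in SAP 3.2 belong to the primary endpoint. That figure does reproduce (47 per arm, difference 1.1, SD 1.75, two-sample t test: 85.4% power), but nothing here depends on it.

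**Step 1: who enters the test.** The tested time is start of weaning minus start of ventilation. A never-ventilated patient has neither time, and no zero is assigned. If no patient on drug is ventilated, the test cannot be run at all. At an assumed 5% rate that has probability 0.95^55 = 0.06.

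**Step 2: a worked example (invented times).** Placebo: 10 of 55 ventilated, at 12, 18, 24, 30, 48, 60, 72, 96, 120 and 144 h. Drug: the five shorter cases are averted and the five longer remain.
- Median among the ventilated: drug 96 h, placebo (48 + 60)/2 = 54 h. The drug looks worse.
- Mean per randomised patient: drug 492/55 = 8.9 h, placebo 624/55 = 11.3 h. The drug looks better.

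**Step 3: simulation, equal durations once ventilated.** Assumptions: 55 per arm, log-normal times with log-SD 0.9 in both arms, no deaths, 4,000 trials per case, normal-approximation Wilcoxon test run when at least 5 patients are ventilated. The table gives the percentage of trials significant in favour of the drug.

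| Ventilated, placebo vs drug | Planned test | All ITT, zeros |
|---|---|---|
| 25% vs 5% | about 2% | about 86% |
| 20% vs 5% | about 1% | about 69% |
| 10% vs 5% | about 0.4% | about 14% |
| 5% vs 2% | near 0% | about 6% |

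Repeat runs moved these by one or two points at most. At 5% vs 2% the expected number ventilated is 55 × 0.05 + 55 × 0.02 = 3.85, and about two thirds of trials fall under the 5-patient rule.

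**Step 4: simulation, shorter cases averted.** The planned test is significant against the drug in 14% (20% vs 5%), 22% (25% vs 5%), 4% (15% vs 2%) and 30% (30% vs 10%) of trials when one latent severity drives both the need for ventilation and its length. If exactly the shortest cases are averted, the figures are about 34%, 46%, 10% and 64%. If a random half of cases is averted at a 20% placebo rate (log-SD 1.0), the planned test is significant for harm in 2.4% and for benefit in 2.1%, which is what chance alone gives.

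**Step 5: error rate of the alternative.** With no drug effect and a 20% rate in both arms, the all-ITT test rejects in 2.2% + 2.6% = 4.8% of trials.

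**Step 6: the 5-patient minimum.** With n ventilated patients split as evenly as possible (k in one arm), the smallest exact two-sided P is 2/C(n,k): 2/10 = 0.20 at n = 5, 2/20 = 0.10 at 6, 2/35 = 0.057 at 7 and 2/70 = 0.029 at 8. An exact test on 5 to 7 ventilated patients could not reach 0.05. The SAP does not say whether the test is exact, and an uncorrected normal approximation can reach 0.0495 at n = 6.

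**The case against.** **The restriction is inferred.** Sections 8.2.4, 8.2.5, 8.2.7 and 8.2.8 state their subsets outright; 8.2.9 does not, and its table is labelled ITT. This stands in part: the authors may have intended zeros. But the definition in 6.1.7.8 allows none, and the label proves little, because kidney Table 14.2.9.1 is also labelled ITT although 8.2.7 restricts it. The text needs a sentence either way.

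**Prevention is credited elsewhere.** A reader might infer that the trial gives no credit for averted ventilation. The documents do not support that. Section 8.2.9 reports the number and percent ventilated by arm. Respiratory failure takes the top pulmonary grade (Protocol Appendix B) and respiratory paralysis scores 3 in the nervous system section (Protocol 10.3.1.1). Both sections enter the primary endpoint and the SSS-AUC, and mortality is analysed separately. The fault lies in this one test.

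**Apparent harm is conditional.** It needs mainly the shorter cases to be averted. With random prevention the test just misses the benefit.

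**Some patients are ventilated before the first dose.** For them ventilation is a baseline feature that treatment cannot change. This stands, and limits the concern to ventilation begun after dosing.

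**The gain may be small.** SAP 8.2.2 explains that neurologic outcomes were not chosen as primary or key secondary endpoints "because of the unexpectedly small number of severely neurotoxic patients enrolled in the trial". If ventilation was rare too, the lower rows of the table apply and the all-ITT test also has little power. This stands.

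**ICU stay.** A reader might infer the same fault in 8.2.10. The documents do not support that: a sum over episodes is zero for a patient with none, and nothing there conditions on admission.

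**Conclusion.** The point holds for the single test in SAP 8.2.9. As written it compares subsets formed partly after randomisation, on a variable that differs from the named endpoint, and it cannot show that ventilation was prevented.

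Its size depends on rates the documents do not give. With 55 per arm and equal durations, the loss is large if ventilation is common on placebo and much reduced on drug (about 1% against 69% at 20% vs 5%), modest at 10% vs 5% (about 0.4% against 14%), and slight at 5% vs 2%, where most trials would be descriptive only. Misleading results against the drug occur only if the averted cases are mainly the shorter ones.

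The endpoint is exploratory and outside the fixed testing sequence, so no confirmatory conclusion changes. The change is still worth making: it is cheap, restores the randomised comparison and brings the test into line with the endpoint's name.

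**What to change.** In SAP 8.2.9:
- Run the Wilcoxon test over all ITT patients on the total duration defined in 6.1.7.9, with 0 hours for patients never ventilated.
- State how deaths before Day 28 are ranked, for example as worst rank. Without this, a patient who dies unventilated would receive the best rank, and one who dies soon after intubation a short duration.
- Show the number and percent ventilated by arm beside the P value.
- Keep time to weaning among ventilated patients as a descriptive summary without a P value.

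In SAP 8.2.10, only confirm that no ICU stay counts as 0, as the sum in 6.1.7.10 implies.

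The cost is a few SAP sentences and no new data. The downsides are many ties at zero, which make the P value hard to read without the percentages beside it, and little power if few patients are ventilated. The 5-patient rule can stay.
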